6.4.5. Week 22 Visit \pm 3 days (Day 155)

The following procedures will be performed at the Visit:

- Record concomitant medication taken
- Adverse Events assessment
- Blood samples will be collected for D2O labeling
- Urinary pregnancy test (for women of childbearing potential only [WOCBP])
- Dispense Deuterated water. Instruct patient to drink 50ml of deuterated water 3 times per day starting on Day 155 for 7 consecutive days (until day 162).
- Blood sample for kinetic biomarkers analysis (patients should be instructed to fast the evening prior to the visit to ensure a 10-hour fast)

Patients will return for blood sampling for kinetic biomarker analysis at 22weeks/ \pm 3 days), Day 158, Day 162 (\pm 1 day), and at day 169 (Week 24).

6.4.6. Week 24 Visit \pm 1

The following procedures will be performed at the visit:

- Complete physical examination
- 12-lead ECG
- Record vital signs
- Record weight, BMI

- Record concomitant medication taken
- MRE (may be done within ± 5 days of the visit)
- Fibroscan
- Adverse Events assessment
- Blood samples will be collected
- Urine samples will be collected for Urinalysis
- Urinary pregnancy test (for women of childbearing potential only [WOCBP]).
- Review study drug compliance and drug administration instructions with subject
- Reconcile study drug administration using pill counts

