6.5.2. Early Termination (ET)

Patients who have discontinued from the study after the first dose of study medication and for any reason will have the following procedures completed:

- Complete physical examination
- Record vital signs
- Weight, BMI
- ECG
- Record concomitant medication taken
- MRE (may be done within ± 5 days of the visit)

- Fibroscan
- Adverse Events assessment
- Blood samples will be collected
- Urine samples will be collected for Urinalysis
- Urinary pregnancy test (for women of childbearing potential only [WOCBP])
- Review study drug compliance with subject
- Reconcile study drug administration using pill counts
- Documentation if Early Termination is due to COVID-19 related AE or concerns.

6.5.3. **Unscheduled Visits**

An unscheduled visit is defined as any visit to the study unit outside of the protocol-evaluation time points where the patient is seen by study unit personnel, e.g., when follow-up assessments are required for safety reasons or when repeat measurements are required out of the screening period (either to confirm a measurement or in case of errors, measuring device failure, etc.).

Unscheduled visits will be needed for patients who may require further follow-up due to safety.

6.6. **Missed or Partially Completed Visits due to COVID-19**

If a subject is unwilling or unable to complete regularly scheduled visit(s) due to COVID-19, the study team will document the following:

- Was the visit partially completed (some procedures completed, while other protocol directed procedures were not completed)? If so:
 - Clinical safety lab tests (hematology, coagulation, pregnancy test, and biochemistry), as required by the visit schedule, must be completed to dispense NTZ to the patient for continued safety monitoring.
- Was any part of the visit performed via a virtual method (e.g. phone, or other technology)? These procedures must be clearly documented as being done “virtually” in the source documentation.
- Description why the visit was partially completed or missed.
- Any COVID-19 related symptoms defined below since the last visit, to include AE onset date, description and resolution date:
 - Fever
 - Cough

- Shortness of breath
- Other symptom as defined by the Centers for Disease Control and Prevention.

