6.6.1. Pre-specified Patient Discontinuation rules

If a patient experiences a Grade IV Common Terminology Criteria for Adverse Event (CTCAE) or meets liver injury criteria as listed in section 6.6.3., the study drug should be interrupted. After causality assessment by the DSMB, if the AE or lab abnormality is considered unrelated to study drug, and the event has resolved or returned to baseline, then the study drug may be re-

started. If the event reoccurs after restart of study drug, then the study drug will be permanently discontinued.

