6.6.3. Dose Adjustment

Enrolled subjects who experience treatment emergent adverse events should be monitored closely and may have the NTZ dose adjusted at the Principal Investigator's discretion.

Enrolled subjects who experience a possible treatment emergent adverse event will be assessed for symptoms and further biochemical assessments as follows:

- GI Adverse Events: the subject will be assessed for abdominal pain, loss of appetite, nausea and vomiting. Blood will be collected for amylase and lipase assessment to rule out pancreatitis.
- Kidney Function Adverse Events: the subject will have blood samples collected for eGFR to rule out kidney dysfunction.
- Musculoskeletal Adverse Events: the subject will be assessed for fatigue, muscle aches and pain. Blood samples will be collected for Creatine Kinase.

The following procedure will be followed for dose adjustments:

1. Patients will be asked to hold drug for 3 days
2. After the 3-day drug hold, patients will be reassessed for adverse event symptoms.
 - If the AE symptoms have resolved following 3 days of drug hold, the patient will discontinue NTZ dosing permanently and will be followed per the schedule of assessments.

If the AE symptoms have not resolved following 3 days of drug hold, the patient will be restarted on a reduced dose of 500 mg NTZ, once a day for 7 days. Patients will be evaluated for treatment emergent adverse events and consideration for resuming the dosage of 500mg NTZ twice a day. PI may determine that the patient should remain at the 500 mg NTZ once a day dose following 7 days of reduced dose. In such scenarios, the patient will be monitored and consideration for resuming the dosage of 500 mg NTZ twice daily will be evaluated at each subsequent visit.

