6.8.2. Assessment of newly synthesized proteins

Kinetic biomarkers will be analyzed to evaluate the pharmacodynamic effect of NTZ on fibrogenesis. Blood samples analyses will be performed after deuterated water intake before and after 24 weeks of treatment. The assessment will involve the analysis of the change (absolute and relative) from baseline between the post-dose and pre-dose deuterated water loading periods.

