8.1.2. Secondary Endpoints

The secondary endpoints are:

- To assess the % change in FSR from baseline to end of treatment (24 weeks of treatment)
- To assess the change in liver stiffness by MRE from baseline to 12 weeks and 24 weeks of treatment
- To assess the change in liver stiffness by fibroscan from baseline to 24 weeks of treatment
- To assess the change from baseline to 12 weeks and 24 weeks of treatment of fibrosis serum biomarkers and scores

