2 STUDY OVERVIEW

2.1 Study Objectives and Endpoints

Primary	
Objective	Endpoint
To evaluate the safety and tolerability of NTZ 500 mg twice daily (BID) after 24 weeks of treatment in patients with non alcoholic steatohepatitis (NASH)-induced stage 2 or stage 3 fibrosis.	Adverse events (AEs) including treatment-emergent AEs (TEAEs) and serious AEs (SAEs), laboratory evaluations, vital signs, electrocardiograms (ECGs), and physical examinations.
Secondary	
Objective	Endpoint
To determine the effect of oral administration of NTZ 500 mg BID on de novo collagen synthesis through Fractional Synthesis Rate (FSR) of circulating plasma proteins in patients with NASH induced stage 2 or stage 3 fibrosis.	Percent change in FSR from baseline to end of treatment (24 weeks of treatment).
To assess changes in liver stiffness as measured by FibroScan® and by Magnetic Resonance Elastography (MRE).	Observed change in liver stiffness by FibroScan from baseline to 24 weeks of treatment Observed change in liver stiffness by MRE from baseline to 12 weeks and 24 weeks of treatment.
To assess the change from baseline in non-invasive markers of fibrosis: ELF™ test score, PIIINP, Hyaluronic acid, CK18, TIMP-1, YKL-40, Alpha 2 macroglobulin, miRNA, ProC3, ProC6, FGF19, and FGF21.	Observed change in non-invasive biomarkers of fibrosis from baseline to 12 weeks and 24 weeks of treatment.
To assess changes in additional non-invasive tests: fibrosis scores: non alcoholic fatty liver disease (NAFLD) fibrosis score and FIB-4.	Observed change in fibrosis scores from baseline to 12 weeks and 24 weeks of treatment.

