3.4 Efficacy Assessments

3.4.1 Fractional Synthesis Rate

FSR of circulating plasma proteins will be measured at baseline and after 24 weeks of treatment. The observed change and percent change in FSR from baseline to Visit 10 Week 24 between the first and second deuterated water loading periods will be assessed to determine the effects of NTZ 500 mg BID on de novo collagen synthesis in the Full Analysis Set.

Wilcoxon signed-rank test will be used for statistical inference. Summary statistics of change in FSR (observed change and percent change) from baseline in FSR will be reported and evaluated at a significance level of 0.05. The p-value from Wilcoxon signed rank test will be reported. Only subjects with FSR at both baseline and Visit 10 Week 24 will be included in analysis. Liver Stiffness

FibroScan

Summary statistics for liver stiffness as measured by FibroScan will be provided at baseline and Visit 10 Week 24/Early Termination, including the change from baseline, based on the Full Analysis Set.

Student's T-test will be used for statistical inference. Summary statistics of change in liver stiffness as measured by FibroScan from baseline in FSR will be reported and evaluated at a significance level of 0.05. The 95% confidence interval (CI) and p-value from Student's T-test will be reported. Only subjects with FibroScan at both baseline and Visit 10 Week 24/Early Termination will be included in analysis.

MRE

Summary statistics for liver stiffness as measured by MRE will be provided at baseline, Visit 4 Week 12, and Visit 10 Week 24/Early Termination, including the changes from baseline, based on the Full Analysis Set. Student's T-test will be used for statistical inference in the same manner as for FibroScan.

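### Patients who stop NTZ under the dose-hold rule can still be labelled at Week 22, and the SAP plans no analysis of FSR change limited to patients on drug in that window

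*SAP*

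**What the plan says.** **Who stays on schedule.** Protocol 6.6.3 sets a 3-day drug hold for a possible treatment-emergent adverse event. If symptoms resolve in the hold, "the patient will discontinue NTZ dosing permanently and will be followed per the schedule of assessments". If they do not, the patient restarts at 500 mg once daily and may stay there at the investigator's discretion.

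**What the schedule does at Week 22.** Protocol 6.4.5 dispenses deuterated water with no condition that the patient is still taking NTZ: "Instruct patient to drink 50ml of deuterated water 3 times per day starting on Day 155". Blood for FSR is drawn on Days 155, 158, 162 and 169.

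**What the analysis includes.** SAP 3.4.1 works in the Full Analysis Set: "Only subjects with FSR at both baseline and Visit 10 Week 24 will be included in analysis". SAP 3.1.6 analyses data as observed. SAP 3.2 defines only a Full Analysis Set and a Safety Analysis Set, with no on-treatment or per-protocol set.

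**How the result is described.** Protocol 8.1.2 and SAP 2.1 describe the endpoint as percent change to the end of 24 weeks of treatment. SAP 3.4.1 attributes the change to NTZ 500 mg BID. Protocol 6.8.2 states the purpose: "Kinetic biomarkers will be analyzed to evaluate the pharmacodynamic effect of NTZ on fibrogenesis".

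**The concern.** FSR here is not a cumulative measure. Each value comes from one labelling period, and the second runs from Day 155 to Day 169. A patient who stopped at the Week 4 visit (Day 29) would have been off NTZ for 155 − 29 = 126 days, or 18 weeks, when the second labelling starts. That value would still enter the analysis as a 24-week result on 500 mg BID.

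If NTZ lowers collagen synthesis and the effect fades after stopping, such values pull the estimated change toward zero. The trial has a single arm of 20, and FSR is its most direct measure of antifibrotic action. The planned tables of FSR change would not separate weak pharmacology from patients who were not taking the drug when it was measured.

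**Working it through.** **Step 1. Which stoppers have a Week 24 FSR?**

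| Route | What the protocol says next | Week 24 FSR? |
|---|---|---|
| 6.6.3, symptoms resolve in the hold | Permanent stop, visits continue | Yes, on the plain reading |
| 6.6.3, symptoms persist | Once daily, possibly for longer than 7 days | Yes, possibly on half the daily dose |
| 6.6.1, event recurs after restart | "then the study drug will be permanently discontinued"; follow-up visits not stated | Unclear |
| 6.5.2, "Patients who have discontinued from the study after the first dose of study medication and for any reason" | Early Termination visit, with no labelling and no FSR sample | No |

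SAP 3.1.2 combines Early Termination visits with Week 24 where applicable. That does not bring off-drug values into FSR, because none is measured at that visit.

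Sections 6.6.1 and 6.6.3 also treat a resolved event differently. Under 6.6.1, drug may restart once an event judged unrelated has resolved. Under 6.6.3, resolution in the hold leads to a permanent stop, and non-resolution leads to a restart at a reduced dose. The sponsor must reconcile these passages, and the number of off-drug patients labelled at Day 155 depends on the outcome.

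**Step 2. Inputs.** From the documents: n = 20 (SAP 2.2.4, based on clinical assessment) and alpha 0.05 (SAP 3.4.1; taken as two-sided). The documents give no effect size, SD, stopping rate, washout or power, so there is no stated figure to reproduce. My assumptions are:
- an on-drug mean effect of d = 0.66 SD, which gives a paired t-test 80% power at n = 20 and serves only as a scale;
- k of the 20 off drug in the second window;
- a share r of the effect remaining in them.

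**Step 3. Mean effect.** Retained fraction = 1 − k(1 − r)/20. With r = 0, each off-drug patient removes 1/20 = 5%. A true 20% reduction in FSR would read as 19, 18, 17 or 16% with k = 1, 2, 3 or 4.

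**Step 4. Power, paired t, r = 0.** With f = k/20, the pooled mean is d(1 − f) and the pooled SD is √(1 + f(1 − f)d²). For k = 2 the mean is 0.66 × 0.90 = 0.594 and the SD is √(1 + 0.09 × 0.4356) = 1.019. The standardized effect is 0.583, and noncentral-t power at n = 20 is 70%. The comparator is the on-drug subset, with effect 0.66 and n = 20 − k.

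| k off drug | Kept (n = 20) | On-drug only (n = 20 − k) | Difference, points |
|---|---|---|---|
| 1 | 75.0% | 77.7% | 2.7 |
| 2 | 69.6% | 75.2% | 5.6 |
| 3 | 64.0% | 72.4% | 8.4 |
| 4 | 58.2% | 69.4% | 11.2 |
| 5 | 52.4% | 66.2% | 13.8 |

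**Step 5. The planned test.** SAP 3.4.1 names the Wilcoxon signed-rank test. Simulation (10,000 runs, normal changes, same d and r = 0) gives about 78% with k = 0. For k = 1 to 4 it gives 73, 68, 63 and 56% kept, against 76, 73, 69 and 66% on-drug only. The pattern is the same.

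**Step 6. If the effect persists.** With r = 0.5, paired-t power is 75.4% kept against 75.2% on-drug only at k = 2, and 67.9% against 66.2% at k = 5. Exclusion gains nothing. With r = 1 there is no dilution.

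**Step 7. Would it arise at all?** If each of 20 patients had a 5 to 20% chance (assumed) of stopping by the 6.6.3 route before Day 155, the chance of at least one would be 1 − 0.95²⁰ = 64% to 1 − 0.80²⁰ = 99%.

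**The case against.** Analysing everyone with data, whether or not they stayed on drug, is a legitimate treatment-policy choice. FSR is secondary in an uncontrolled safety study, and a subset selected on tolerating NTZ does not isolate a drug effect. SAP 3.4.4 already allows further exploratory work. All of this stands, and it is why the Full Analysis Set result should remain the main one. It does not remove the gap: the SAP does not name that choice, and it adds nothing for a question framed as pharmacodynamic.

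Four stronger readings are tempting, and the documents do not support them.

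- *Every patient who stops NTZ enters the Week 24 FSR analysis.* Only the 6.6.3 route says so. Section 6.6.1 is silent, and patients who leave the study have no FSR at Early Termination.
- *Dilution is certain, and analysing only on-drug patients would restore all the lost power.* Dilution needs a real effect that wanes, and the documents hold no washout data. The subset loses power too: at k = 5 the fall from 80% to 52% is 28 points, of which the subset recovers about 14.
- *A null result could not be interpreted.* SAP 3.3.6 tabulates exposure to the last dose in 4-week bands, SAP 3.5.1 lists adverse events leading to withdrawal from study drug, and SAP 7 lists all data by subject. With 20 patients, a reader could find those who stopped permanently before Day 155. Interruptions and once-daily dosing are harder to see, because the exposure figure ignores interruptions.
- *The same restriction belongs on MRE, FibroScan and serum markers.* Days 155 to 169 are the FSR labelling window. Nothing in the documents justifies using it for the other measures.

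**Conclusion.** The point holds in a limited form. At least one explicit route leads from a permanent stop to labelling at Day 155 and into an analysis described as the effect of 500 mg BID. No planned analysis of FSR change shows the on-drug patients separately.

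The size cannot be fixed from the documents. If the effect is fully lost after stopping, each such patient among 20 costs 5% of the mean effect. At an assumed 0.66 SD, keeping 1 to 5 of them rather than analysing on-drug patients only costs about 3 to 14 points of paired-t power. If half the effect persists, it costs nothing. These figures also assume that all 20 patients have both FSR values. SAP 3.1.5 disclaims formal hypothesis testing, so power serves here only as a scale of the loss. This is an inexpensive improvement to the plan; the Full Analysis Set analysis itself is not in error.

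**What to change.** Keep the Full Analysis Set analysis of FSR as the main result, and say that it includes patients regardless of stopping or dose reduction. In SAP 3.4.1, before database lock:

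1. Prespecify one supportive analysis of FSR change in patients taking NTZ throughout Day 155 to Day 169, with a stated rule for short interruptions. Show it with and without patients on once-daily dosing in that window.
2. Report how many patients were on BID, on once daily and off drug at the second loading.

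The sponsor should also reconcile Protocol 6.6.1 with 6.6.3 and state whether patients stopped under 6.6.1 are labelled and sampled at Week 22.

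The cost is SAP wording and one repeated table. The last-dose date is on the end of study form (SAP 3.3.6), interruptions are documented (Protocol 5.5), and dose regimen is in the source records (Protocol 9.6). One check is needed: the action-taken list in Protocol 7.2.3 has no entry for a reduced dose, so confirm that once-daily dosing reaches the analysis data. The downside is that the subset is smaller and selected on tolerating the drug, so it can only be supportive.

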3.4.2 Non-invasive Markers of Fibrosis

Biomarkers of fibrosis include ELF test score, PIIINP, Hyaluronic acid, CK18, TIMP-1, YKL-40, Alpha 2 macroglobulin, miRNA, ProC3, ProC6, FGF19, and FGF21.

Summary statistics for biomarkers will be provided at baseline, Visit 4 Week 12, Visit 10 Week 24/Early Termination, and at end of study (EOS) Week 28, including the changes from baseline, based on the Full Analysis Set. Student's T-test will be used for statistical inference in the same manner as for FibroScan.

3.4.3 Fibrosis Scores

NAFLD Fibrosis Score

Summary statistics for NAFLD fibrosis score will be provided at baseline, Visit 4 Week 12, and Visit 10 Week 24/Early Termination, including changes from baseline, based on the Full Analysis Set. Student's T-test will be used for statistical inference in the same manner as for FibroScan.

FIB-4

Summary statistics for FIB-4 will be provided at baseline, Visit 4 Week 12, and Visit 10 Week 24/Early Termination, including changes from baseline, based on the Full Analysis Set. Student's T-test will be used for statistical inference in the same manner as for FibroScan.

3.4.4 Exploratory Analysis

Additional serum and plasma samples will be maintained for future analysis. Exploratory measures for magnetic resonance imaging (MRI)/MRE sequence development will be maintained for future analysis.

Exploratory scatter plots will be provided for FSR vs. ProC3, FSR vs. liver stiffness as measured by MRE, and FSR vs. ELF test score, including the Pearson Correlation Coefficients and p-values. Additional exploratory analyses may also be performed to evaluate the association of individual exploratory biomarkers or combination of biomarkers with clinical measurements and other risk factors.

3.5 Safety Assessments

3.5.1 Adverse Events

All AEs regardless of seriousness or relationship to study drug, including those occurring during the Screening Period, are to be recorded on the corresponding page(s) of the CRF and in the patient's medical record from the informed consent form signature until study end for each patient. All AEs will be coded to system organ class and preferred term using Medical Dictionary for Regulatory Activities (MedDRA) version 21.0.

TEAEs are defined as AEs that worsen in severity or relationship to study drug or commence on or after the time of start of first study drug administration. This may include AEs that start during follow-up after the last dose of study drug.

Study drug related AEs are defined as AEs that are possibly related or related.

An overview of AEs based on the Safety Analysis Set will be provided including counts and percentages of subjects with the following:

- Any TEAEs (overall and by maximum severity)
- Any study drug related TEAEs (overall and by maximum severity)
- Any SAEs
- Any study drug related SAEs
- Any deaths due to AEs
- Any AEs leading to withdrawal from study or study drug
- Any study drug related AEs leading to withdrawal from study or study drug

Counts and percentages of subjects will also be presented by system organ class and preferred term for TEAEs and study drug related TEAEs. In addition, summaries will be provided by system organ class, preferred term, and maximum severity.

Listings will be presented specifically for SAEs and TEAEs leading to withdrawal from study or study drug.

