7.2.2. Relation to the study treatment

The Investigator will make a clinical and scientific judgment regarding whether or not the AE was related to study treatment. The Investigator will evaluate any changes in laboratory values, make a determination as to whether or not the change is clinically important, and whether or not the changes were related to study drug. However, even if the Investigator feels there is no relationship to the study drug, the AE or clinically significant laboratory abnormality must be recorded in the eCRF.

The Investigator will record the relation to the study treatment according to the following causality terms:

- Related: the AE follows a reasonable temporal sequence from the time of drug administration and it cannot be explained by the patient's clinical state or the study procedures/conditions. The AE abates upon discontinuation of the study drug and reappears when the study drug is introduced.
- Possibly related: the AE follows a reasonable temporal sequence from the time of drug administration, but could have been produced by the patient's clinical state or the study procedures/conditions.

- Unlikely related: the temporal association between the AE and the study drug is such that the study drug is not likely to have any reasonable association with the AE. The relationship is not likely because of other plausible explanations.
- Not related: the AE must definitely be caused by the patient's clinical state or the study procedure/conditions. A reasonable explanation must be given, e.g., no investigational product taken, preplanned elective medical intervention, or incompatible temporal relationship.
- Not assessable: the report suggesting an adverse reaction cannot be judged because information is insufficient or contradictory and data cannot be supplemented or verified.

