8.5.1. Adverse Events

Treatment-emergent adverse events (TEAEs) are defined as AEs that worsen or commence on or after the time of start of first study drug administration. AEs, including SAEs, will be coded using MedDRA. The number and percentage of subjects experiencing TEAE, including TEAEs leading to study drug discontinuation and SAEs, will be summarized for each system organ class (SOC) and Preferred Term. In addition, AEs will be tabulated according to severity, causality, and relation to the study drug.

Individual data listings for AEs will be presented for each subject.

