3.1.6 Handling of Dropouts and Missing Data

All data will be analyzed as observed. Dropouts and missing data will not be imputed.

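### Adverse events rated Not assessable drop out of every drug-related count, and the SAP omits the causality table that would show them

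*SAP*

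**What the plan says.** Protocol 7.2.2 gives a closed list: "The Investigator will record the relation to the study treatment according to the following causality terms". The five terms are *Related*, *Possibly related*, *Unlikely related*, *Not related* and *Not assessable*. The last is worded "Not assessable: the report suggesting an adverse reaction cannot be judged because information is insufficient or contradictory", and the same sentence adds that the data cannot be completed or checked.

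SAP 3.5.1 then sets the rule for the summaries: "Study drug related AEs are defined as AEs that are possibly related or related". Three of the seven lines of the AE overview use it: "Any study drug related TEAEs (overall and by maximum severity"), drug-related SAEs, and drug-related AEs leading to withdrawal. So does the table of drug-related TEAEs by system organ class and preferred term. The other four overview lines do not use it: "Any TEAEs (overall and by maximum severity"), any SAEs, deaths due to AEs, and any AEs leading to withdrawal.

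Protocol 8.5.1 promises more: "In addition, AEs will be tabulated according to severity, causality, and relation to the study drug". SAP 3.5.1 specifies no table by causality category, while SAP section 6 states that nothing has changed from the protocol. SAP 3.1.6 says "Dropouts and missing data will not be imputed" and does not mention causality ratings.

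**The concern.** *Not assessable* is not a negative judgement. By the protocol's own definition it begins with a report that raises suspicion and ends without enough information to decide. *Unlikely related* and *Not related* both rest on stated reasons against a link. In the drug-related rows, the SAP gives the unresolved suspicion the same treatment as the reasoned negative. This can lower a drug-related count or leave it unchanged. It can never raise one.

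Safety is the primary objective. SAP 2.1 lists as the endpoint "Adverse events (AEs) including treatment-emergent AEs (TEAEs) and serious AEs (SAEs"), together with laboratory tests, vital signs, ECGs and physical examinations. With one arm and no control group, readers will look to the drug-related rows to separate drug effect from background illness. With about 20 subjects, those rows may hold very few people, so one reclassified subject can change none to one.

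**Working it through.** The documents give no drug-related rate and no expected number of *Not assessable* events, so there is no figure of the plan's own to reproduce. The check is a comparison of the texts, followed by simple counting.

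**1. How each term is treated**

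| Term (protocol 7.2.2) | Basis for the rating, paraphrased | In the drug-related count (SAP 3.5.1)? |
|---|---|---|
| Related | Timing fits, no other explanation | Yes |
| Possibly related | Timing fits, another cause could explain it | Yes |
| Unlikely related | Timing argues against, other explanations plausible | No |
| Not related | Another cause is definite, reason required | No |
| Not assessable | Suspicion raised, information too thin or conflicting | No |
| No rating recorded | Not addressed | No, by default |

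**2. Where the excluded events would still appear.** They stay in the four all-causality overview lines, where applicable, and in the subject listings (SAP section 7). No specified summary table shows how many there are.

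**3. Size per affected subject**

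Inputs: N = 20, the planned sample (protocol 8.7, SAP 2.2.4), assuming all are dosed. Let x be the subjects in a row with a *Related* or *Possibly related* event. Let k be the subjects whose only candidate event in that row is *Not assessable*. Both are assumptions.

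- SAP rule: x/20
- *Not assessable* counted as related: (x + k)/20
- Difference: k/20, or 5k percentage points

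With x = 4 assumed:

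| k | SAP rule | Counted as related | Difference |
|---|---|---|---|
| 0 | 4/20 = 20% | 4/20 = 20% | 0 points |
| 1 | 20% | 5/20 = 25% | 5 points |
| 2 | 20% | 6/20 = 30% | 10 points |
| 3 | 20% | 7/20 = 35% | 15 points |

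In a sparse row such as drug-related SAEs, x = 0 and k = 1 would give 0/20 = 0% in place of 1/20 = 5%.

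**4. How often it could occur.** Let q be the chance that a subject is affected. This is assumed, because the documents give no value. With subjects independent, P(at least one of 20) = 1 − (1 − q)^20, and the expected shift is 20q × 5 points = 100q points.

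| q | P(at least one affected) | Expected shift |
|---|---|---|
| 1% | 18% | 1 point |
| 2% | 33% | 2 points |
| 5% | 64% | 5 points |
| 10% | 88% | 10 points |

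**The case against.** The strongest reply is that this may never arise. The protocol reserves *Not assessable* for data that cannot be completed or verified, which makes it a last resort. The trial has one site, is open label, and sees patients at least every four weeks on treatment. Protocol 7.3.4 requires AEs to be followed to resolution or stabilisation. Few such ratings should remain, although protocol 6.6 does foresee missed, partial and virtual visits during COVID-19. This stands as a limit on the likely frequency. It does not supply a rule for the events that remain.

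A reader might infer three stronger things that the documents do not support:

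- *That the drug-related rates are biased downward as a matter of fact.* A shift needs a subject with a *Not assessable* event and no other qualifying event in the row. For the shift to be bias rather than a difference in labelling, the drug must also have caused the event.
- *That the SAP declares these events unrelated.* It defines a related subset and plans no table of unrelated events. Their exclusion follows from that definition.
- *That causality attribution is the trial's only comparison.* SAP 3.5.2 to 3.5.5 plan changes from baseline for laboratory tests, vital signs and ECGs, shift tables for ALT, AST, CK and bilirubin, and physical examination findings by visit. The DSMB also judges causality for events that trigger the stopping rules.

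It is also fair to say that the endpoint in SAP 2.1 does not mention relatedness, that no confidence interval is planned for AE rates, and that SAP 3.1.5 rules out formal hypothesis testing. No planned test or decision therefore turns on these rows.

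Finally, counting *Not assessable* as related is a convention that overstates relatedness where the drug was not the cause. A separate row would be an alternative. A footnoted count answers most of this, since it shows the figure both ways.

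**Conclusion.** The point holds in a limited form. The stated rule leaves *Not assessable* events out of all drug-related rows, and its effect can only be downward or nil. The planned summary tables do not reveal this, because the causality tabulation in protocol 8.5.1 is missing from the SAP while section 6 reports no changes. The possible understatement is 5 percentage points per affected subject, assuming 20 dosed subjects. The number affected is unknown and may be zero. The all-causality rows are intact, and no test or sample size depends on the result. The wording that the documents support is *may understate*, not *biases*. It is worth correcting before the ratings are tabulated, so that the rule is not chosen with the counts in view.

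**What to change.** Before database lock, amend the SAP as follows:

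- In 3.5.1, count AEs rated *Not assessable*, and AEs with no causality rating, as study drug related in the summary rows.
- Footnote each affected row with the number of subjects who are in it only for one of these two reasons, given separately, so that the count without them can be read off.
- Add the tabulation by causality category from protocol 8.5.1. This also makes the statement in section 6 correct on this point.
- State that the treatment of unrated events is a classification rule and an exception to the no-imputation statement in 3.1.6.

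The cost is a few sentences, one programming condition, the footnotes and one table. The price is a drug-related rate that may be slightly less favourable and may include some events that the drug did not cause.
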